## **9. STATISTICAL METHODOLOGY**

### **9.1 General**

Data listings will be provided for all data that is databased. Summary statistics and statistical analysis will only be presented for data where detailed in this SAP. For continuous data, summary statistics will include the arithmetic mean, arithmetic standard deviation (SD), median, min, max and N; for log-normal data (e.g. the PK parameters: area under the concentration versus time curve [AUCs] and maximum observed drug concentration [ $C_{max}$ ]) the geometric mean and geometric coefficient of variation (CV%) will also be presented. For categorical data, frequency count and percentages will be presented. Data listings will be provided for all subjects up to the point of withdrawal, with any subjects excluded from the relevant population highlighted. Summary statistics and statistical analyses will generally only be performed for subjects included in the relevant analysis population. For the calculation of summary statistics and statistical analysis, unrounded data will be used.

Mean change from baseline is the mean of all individual subjects' change from baseline values. Each individual change from baseline will be calculated by subtracting the individual subject's baseline value from the value at the timepoint. The individual subject's change from baseline values will be used to calculate the mean change from baseline using a SAS procedure such as Proc Univariate.

Data from subjects receiving placebo in the IV cohorts will be pooled to form 1 placebo group. Data will be also summarized by population (overall, Japanese and Caucasian) where appropriate. The clinical chemistry and hematology, vital signs, and electrocardiogram (ECG) data will only be summarized by population if a trend is observed.

Data analysis will be performed using SAS® Version 9.4.

## 9.2 Demographics and Subject Disposition

Subject disposition will be listed. The demographic variables age, sex, population, ethnicity, race, body weight, height and body mass index (BMI) will be summarized by population and treatment and listed. All other demographic data will be listed only.

## 9.3 Pharmacokinetic Assessment

### 9.3.1 Pharmacokinetic Analysis

The PK parameter estimates for LY3074828 will be calculated by standard noncompartmental methods of analysis.

The primary parameters for analysis will be  $C_{max}$  and area under the concentration versus time curve from zero to infinity [AUC(0- $\infty$ )] of LY3074828. Other noncompartmental parameters, such as half-life, clearance, and volume of distribution (apparent clearance and apparent volume of distribution for SC administration) may be reported.

### 9.3.2 Pharmacokinetic Statistical Methodology

The PK parameter estimates following IV administration will be evaluated to delineate effects of dose proportionality. Log-transformed  $C_{max}$  and AUC(0- $\infty$ ) estimates will be evaluated in a power model with log-transformed dose as the explanatory variable. The treatment differences will be back-transformed to present the ratios of geometric means and the corresponding 90% confidence interval (CI).

Example SAS code 1:

```
proc mixed data=pk;
  by parameter;
  model lpk = ldose / alpha=0.1 residual ddfm=kr;
  estimate 'xx mg' intercept 1 ldose yy / cl; /* Log value of xx */
  estimate 'zz mg - xx mg' ldose pp / alpha=0.1 cl; /* Difference in
log values of zz and xx */
  ods output solutionf=est;
  ods output estimates=estims;
run;
```

The above analysis will also be repeated for each population separately to examine the effect of the population on dose proportionality.

For the SC dose, the bioavailability relative to IV infusion at the same dose will be evaluated via a log-transformed model. The log-transformed  $C_{max}$  and AUC(0- $\infty$ ) will be the response variables, and route of administration (IV or SC) is the explanatory variable and ratio (SC/IV), and its 90% CI will be calculated based on the model to assess the absolute bioavailability.

Example SAS code 2:

```
proc mixed data=pk;
```

```
by parameter;
class route;
model log_pk = route / residual ddfm=kr;
lsmeans route / alpha=0.1 cl pdiff;
ods output lsmeans=lsmeans;
ods output diffs=diffs;
run;
```

Additional analysis will be conducted if deemed appropriate.

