Therefore, this study planned to evaluate the safety, tolerability, and PK of a 1200-mg IV dose of LY3074828. The 1200-mg IV dose cohort (Cohort 5) was dosed after safety, tolerability, and PK data were confirmed from the 600-mg dose cohort (Cohort 1). Other dose levels were dosed concurrently in this study because these doses have already been shown to be well tolerated in Study AMAA. Evaluation of 1200-mg IV dose cohort (Cohort 5) provided safety and PK data to support the use of a higher dose level in Study AMAC and Study AMAG.

In addition to the above evaluation, this study is amended to add the evaluation of safety, tolerability, and PK of a 2400-mg IV dose of LY3074828, since there is a possibility to evaluate a higher dose level up to 2400 mg IV in later clinical development. The proposed dose of 2400-mg IV infusion has a sufficient margin of safety in terms of dose. Moreover, the clinical safety profile of LY3074828 available to date supports 2400-mg IV administration in this study. Single doses of up to 1200 mg IV were evaluated in healthy subjects from Study AMAD and no dose-related safety or tolerability issues were observed. Evaluation of the safety data available to date in the ongoing Study AMAC and Study AMAG that are evaluating higher and more frequent dose regimens of up to 1000 mg IV Q4W for up to 52 weeks has not revealed any differences in the safety profile. The PK profile of this drug was found to be approximately linear up to 1200-mg IV administration. Since the 2400-mg IV dose is only 2-fold of 1200 mg, it

is unlikely that an unexpected PK profile will be observed after administration of a 2400-mg IV dose. Therefore, evaluation of this additional higher dose cohort (2400 mg) will provide safety and PK data to support the use of a higher dose level beyond 1200 mg during the clinical development of this compound.

Table AMAD.2. Margin of Safety for Intravenous Administration of 2400 mg LY3074828 Based on Administered Dose and Predicted Exposure

	Dose (mg/kg)	Dose Multiple ^a	AUC _{0-672h,ss} (μ g•h/mL)	Margin of Safety ^b
Human highest dose (2400 mg)^c	36.9 (IV)		110000	
Monkey NOAEL^d 6-month study	100 (SC)	2.7	85800 ^e	0.78
Monkey NOAEL^f 4-week study	100 (IV)	2.7	204200 ^g	1.9

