11.2.4.2. Pharmacokinetic Statistical Inference

PK parameter estimates following IV administration will be evaluated to delineate effects of dose proportionality. Log-transformed C_{max} and AUC estimates will be evaluated in a power model with log-transformed dose as the explanatory variable. The treatment differences will be back-transformed to present the ratios of geometric means and the corresponding 90% confidence interval (CI). Exploratory power model analysis based on the model including race and race-by-dose interaction terms will be also performed to examine the effect of the race on dose proportionality.

For the SC dose, the bioavailability relative to IV infusion at the same dose will be evaluated via a log-transformed model. The log-transformed C_{max} and AUC will be the response variable, and route of administration (IV or SC) is the explanatory variable and ratio (SC/IV), and its 90% CI will be calculated based on the model to assess the absolute bioavailability.

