## 5. STUDY DESIGN

This is a single-site, subject- and investigator-blind, randomized, placebo-controlled, single-dose study to assess the safety, tolerability, and PK of LY3074828 in Japanese and Caucasian healthy subjects. Subjects will be randomized to LY3074828 or placebo within 1 of 6 cohorts, as shown in Figure 1. Cohort 1 will consist of 10 subjects (6 Japanese and 4 Caucasian) who will be randomized so that 5 Japanese subjects and 3 Caucasian subjects will receive LY3074828 while 1 Japanese subject and 1 Caucasian subject will receive placebo. Cohorts 2 through 6 will consist of 8 subjects (4 Japanese and 4 Caucasian) who are randomized in a 3:1 ratio of LY3074828 to placebo. For each cohort, 3 Japanese subjects and 3 Caucasian subjects will receive LY3074828 while 1 Japanese subject and 1 Caucasian subject will receive placebo.

Single doses up to 600 mg IV have been studied and shown to be well tolerated, therefore all cohorts, with the exception of Cohort 5 and Cohort 6, may be dosed in parallel if the site is able to accommodate more than 1 cohort at a time. Cohort 5 will be dosed after confirming the safety and PK data from Cohort 1. Cohort 6 will be dosed last after confirming the safety and PK data from Cohort 5. Two additional Japanese subjects will be included in Cohort 1 to ensure that a sufficient number of Japanese subjects will have received LY3074828 at the time of the interim analysis. An interim analysis is planned based on Cohort 1 data through Day 15 to support Japanese patients being included in the planned global Phase 2 study, Study I6T-MC-AMAC (AMAC).

Abbreviations: FU = follow up; IV = intravenous; SC = subcutaneous

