**Figure. 1 Study design**

## **Treatment**

Five IV dose levels and 1 SC dose level of LY3074828 will be assessed in Cohorts 1 through 6. The following treatments are planned:

Cohort 1: a single dose of LY3074828 600 mg or placebo IV  
Cohort 2: a single dose of LY3074828 200 mg or placebo IV  
Cohort 3: a single dose of LY3074828 200 mg or placebo SC  
Cohort 4: a single dose of LY3074828 60 mg or placebo IV  
Cohort 5: a single dose of LY3074828 1200 mg or placebo IV  
Cohort 6: a single dose of LY3074828 2400 mg or placebo IV

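### The planned power model cannot test whether PK stays linear beyond 1200 mg: each IV dose-to-dose ratio it yields is the dose ratio raised to one fitted slope

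*SAP*

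**What the plan says.** Protocol 11.2.4.2 and SAP 9.3.2 both specify a power model for IV dose proportionality. The protocol's wording is "The treatment differences will be back-transformed to present the ratios of geometric means", and the SAP repeats it: "The treatment differences will be back-transformed to present the ratios of geometric means and the corresponding 90% confidence interval (CI"). SAP example code 1 shows how this is done. The model statement is "model lpk = ldose / alpha=0.1 residual ddfm=kr", with dose as a single continuous term. A difference between two doses comes from "estimate 'zz mg - xx mg' ldose pp / alpha=0.1 cl", which uses the slope and nothing else. The dose-level line in the same code adds the intercept, so it gives a fitted point on the line. The SAP repeats the fit within each population, so there is one slope per parameter overall and one for each population.

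SAP 9.3.2 names no fit with dose as a class factor, no curvature term, no formal lack-of-fit test and no dose-normalised contrast. SAP 9.1 separately provides observed geometric means and geometric CV% for AUC and Cmax.

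On prior knowledge, Protocol 9.3 states: "The PK profile of this drug was found to be approximately linear up to 1200-mg IV administration". It then argues that an unexpected profile at 2400 mg is unlikely because that dose is only twice 1200 mg, and it expects Cohort 6 to provide data supporting doses above 1200 mg.

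**The concern.** The amendment adds one dose. Since PK is described as approximately linear up to 1200 mg, the new PK question is whether 2400 mg stays on that line. The only planned inference across IV doses fits a single line through all five doses and reads every dose-to-dose ratio from it. A reader who sees a ratio of geometric means for 2400 against 1200 mg will take it as a comparison of the two groups. It is a prediction from the slope, and 26 of the 32 subjects who determine that slope were dosed at 1200 mg or below.

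If exposure at 2400 mg departed from the line, the report could carry a tight model-based ratio near 2 beside observed geometric means that say otherwise, with no planned interval for the direct comparison.

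**Working it through.** **Inputs from the documents.** The SAP's Treatment section gives the dose levels: "Five IV dose levels and 1 SC dose level of LY3074828 will be assessed in Cohorts 1 through 6". The IV doses are 60, 200, 600, 1200 and 2400 mg. On active drug, Cohort 1 (600 mg) has 8 subjects: "5 Japanese subjects and 3 Caucasian subjects will receive LY3074828". Each other IV cohort has 6: "For each cohort, 3 Japanese subjects and 3 Caucasian subjects will receive LY3074828". Active IV total: 8 + 4×6 = 32. The plan's headcount reproduces (10 + 5×8 = 50), but the plan states no precision or variability for this analysis.

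**Assumptions.** Neither a between-subject CV nor a departure size is in the documents. I use geometric CVs of 20-35%, with σ = √ln(1+CV²), so σ = 0.246 at CV 25%. The departure is a factor m = 1.25 at 2400 mg only, with exact proportionality below.

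**Slope under a local departure.** With x = ln(dose), the mean is 6.149 and Sxx = 51.50.
- Slope shift per unit of log departure: 6×(7.783 − 6.149)/51.50 = 0.190.
- Share reaching the 2400/1200 ratio: 0.190×ln 2 = 0.13.
- Share reaching the 2400/60 ratio: 0.190×ln 40 = 0.70.
- For m = 1.25: slope = 1 + 0.190×0.223 = 1.042. Reported 2400/1200 = 2^1.042 = 2.06 (true 2.50). Reported 2400/60 = 46.8 (true 50).

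**Width of the 2400/1200 interval.**
- Power model: SE = σ×ln 2/√51.50 = 0.097σ. At CV 25% on 30 df the factor is exp(1.697×0.097×0.246) = 1.04.
- Class-dose fit: SE = σ×√(1/6+1/6) = 0.577σ. At CV 25% on 27 df the factor is exp(1.703×0.577×0.246) = 1.27.
- The ratio of SEs is 6.0. For 2400/60 it is only 0.577/0.514 = 1.12.

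**Dose-normalised 2400 mg against the simple average of the four lower dose means.** SE = σ×√[1/6 + (1/16)(1/6+1/6+1/8+1/6)] = 0.454σ, a factor of 1.21 at CV 25%.

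**Simulation, 20,000 trials per CV, m = 1.25.**

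| | CV 20% | CV 25% | CV 30% | CV 35% |
|---|---|---|---|---|
| Power-model 90% CI covers true 2400/1200 | 0% | 0% | 0% | 0% |
| Power-model 90% CI covers true 2400/60 | 86% | 87% | 88% | 89% |
| Class-dose 90% CI covers true 2400/1200 | 90% | 90% | 90% | 90% |
| Slope 90% CI excludes 1 | 41% | 31% | 25% | 22% |
| Class-dose 2400 vs 1200 excludes proportionality | 60% | 46% | 36% | 30% |
| Class-dose 2400 vs average of 60-1200 excludes proportionality | 78% | 62% | 50% | 41% |
| 3-df lack-of-fit F test, 5% level | 31% | 20% | 15% | 12% |

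At CV 25% the average power-model interval for 2400/1200 runs from 1.98 to 2.15. With m = 1 its coverage is 90% at every CV, so the narrow interval is correct when the power law holds.

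**The case against.** The strongest reply is that the consequence is limited. The PK objectives are to estimate and explore. No acceptance limit or decision rule uses a 2400/1200 ratio, and the doses in the example code are placeholders, so the SAP never names that pair. Adjacent doses are also the model's worst case. All of this stands, and it sets the weight of the point. It does not supply an inference about 2400 mg.

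A reader might infer more than the documents support, in five ways:
- **That every geometric mean ratio in the SAP depends on the slope.** The SC/IV ratio does not: its model has route as a class factor.
- **That the intervals are falsely narrow in general.** They are too narrow only if the power law fails.
- **That a departure would disappear from the report.** Observed geometric means are planned by treatment, 2400 mg is its own treatment group, clearance may be reported, and the model code requests residuals. A departure could be seen, though without a planned interval. The slope would also move somewhat.
- **That the fitted 2400 mg mean carries a planned 90% CI.** The dose-level line in the code has no alpha option, so the 95% default applies. Its coverage in the CV 25% case is about 70%.
- **That no display of dose-normalised exposure exists.** The table and figure shells are a separate document and were not available, so this cannot be confirmed.

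The SAP also allows further analysis if judged appropriate. That leaves the check to be chosen after the data are seen, by a study team that Protocol 11.3 describes as unblinded. It is not a prespecified analysis.

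**Conclusion.** The point holds in a limited form. Every IV dose-to-dose ratio from SAP 9.3.2 is the dose ratio raised to a single slope, whether overall or within a population. A model-based 2400/1200 ratio therefore cannot show whether PK stays linear above 1200 mg. About 87% of a log-scale departure confined to 2400 mg is removed from it. For the assumed 1.25-fold departure the 90% CI is centred near 2.06 instead of 2.50 and almost never covers the truth.

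The 13% and 70% shares follow from the planned doses and numbers alone. The coverage and detection figures rest on the assumed CV, the assumed size of departure, and its confinement to 2400 mg. PK is a secondary objective, but Cmax and AUC(0-∞) are its primary parameters, and the gap concerns the one dose that the amendment adds. The plan should be changed.

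**What to change.** In SAP 9.3.2:
- Keep the power-model slope with its 90% CI as the overall summary of proportionality.
- Add a prespecified fit of log Cmax and log AUC(0-∞) with dose as a class factor, on the same 32 active IV subjects. From it report dose-normalised geometric mean ratios with 90% CIs for 2400 against 1200 mg, and for 2400 mg against the average of 60-1200 mg.
- Take adjacent-dose ratios from this fit, and label the power-model ratios as model-predicted.
- Treat the 3-df lack-of-fit test as supportive only, because it has little power here.

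The cost is one more model call and one table, with no new subjects or samples. Dose-specific intervals become wider: about ×/÷1.27 for 2400 against 1200 mg at CV 25%, which is the precision that six subjects against six can give. The second contrast detects more because it pools the lower doses, so it relies on proportionality from 60 to 1200 mg and should be reported with that condition. Neither contrast gives high power at these numbers.

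### The example code in SAP 9.3.2 contradicts its own output request and interval level and can invert the SC/IV ratio, and the text labels the Cmax ratio as bioavailability

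*SAP*

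**What the plan says.** SAP 9.3.2 describes two models for log-transformed Cmax and AUC(0-∞), each with a block of example code. SAP 9.1 names SAS 9.4 as the software.

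**Dose proportionality, IV cohorts.** This is a power model on log dose. The commitment on intervals reads "The treatment differences will be back-transformed to present the ratios of geometric means and the corresponding 90% confidence interval (CI". The text mentions neither an interval for a dose-level mean nor the slope. Code 1 contains:
- the model, "model lpk = ldose / alpha=0.1 residual ddfm=kr";
- a dose-mean line, "estimate 'xx mg' intercept 1 ldose yy / cl";
- a between-dose line, "estimate 'zz mg - xx mg' ldose pp / alpha=0.1 cl";
- an output request, "ods output solutionf=est".

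The analysis is then repeated within each population.

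**SC against IV at 200 mg.** With both Cmax and AUC(0-∞) as responses, the text says "route of administration (IV or SC) is the explanatory variable and ratio (SC/IV), and its 90% CI will be calculated based on the model". Code 2 declares route in a CLASS statement with no order or reference level, then requests "lsmeans route / alpha=0.1 cl pdiff".

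Protocol 11.2.4.2 describes these power and route models in nearly the same words, without code. SAP section 3 says the SAP supersedes the protocol's statistical considerations and, with the separate TFL shells, serves as the template for the study report.

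**The concern.** These are the only PK models in the SAP for which code is given, and they serve the secondary PK objectives. Four details do not fit together:

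- Code 1 asks for a table that its own MODEL statement does not generate. In a power model that table holds the slope, which is the direct measure of dose proportionality.
- Code 1 gives dose-level means a different confidence level from the ratios in the next line. Code 2 gives its route means 90% limits, so geometric means from the two analyses would also differ in coverage.
- Code 2 leaves the direction of the route contrast to the order of the CLASS levels, although the text fixes the direction as SC over IV.
- The text applies the term absolute bioavailability to Cmax as well as to AUC.

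At stake is a report in which the slope is missing, interval levels differ without notice, a ratio may be printed upside down, and a peak-exposure ratio is read as a bioavailability.

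**Working it through.** **Assumption on software.** The documents do not describe SAS behaviour. The check assumes standard PROC MIXED behaviour: `alpha=` acts per statement; ESTIMATE defaults to 0.05; the SolutionF table needs SOLUTION on MODEL; fixed-effect limits need CL; PDIFF takes the first CLASS level minus the second.

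**Inputs.**
- Active IV subjects: 8 in Cohort 1 and 6 in each of Cohorts 2, 4, 5 and 6, so 8 + 4 × 6 = 32 (SAP 5).
- By population: Japanese 5 + 4 × 3 = 17; Caucasian 5 × 3 = 15.
- 200 mg SC 6 subjects, 200 mg IV 6 subjects.
- From Study AMAA, as reported in Protocol 5.1: SC bioavailability 40%, half-life 10.5 days, SC peak at 3 days.

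**1. The stated 90% level.** The between-dose ESTIMATE and the LSMEANS statement both carry alpha = 0.10, so both promised levels are reproduced.

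**2. Dose-mean limits.** No alpha is set, so the limits are 95%. The multipliers use n − 2 degrees of freedom:

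| Set | df | t for 90% | t for 95% | Ratio |
|---|---|---|---|---|
| All IV | 30 | 1.697 | 2.042 | 1.20 |
| Japanese | 15 | 1.753 | 2.131 | 1.22 |
| Caucasian | 13 | 1.771 | 2.160 | 1.22 |

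In one simulated data set at an assumed CV of 25%, the limits for the 600 mg geometric mean are the mean multiplied or divided by 1.063 at 90% and 1.077 at 95%.

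**3. Slope.** MODEL has alpha = 0.10 but neither SOLUTION nor CL, so that alpha does nothing and SolutionF is not produced. The between-dose estimate equals pp × slope, where pp is the difference in log dose, and its standard error is pp × SE(slope) on the same degrees of freedom. Dividing the estimate and both limits by pp therefore returns the slope and its 90% interval exactly. In the same simulation both routes gave 0.982 (0.934 to 1.029).

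The printed ratio is (dose ratio)^slope. Over 60 to 2400 mg the dose ratio is 40, so slopes of 0.9, 1.0 and 1.1 print as:
- 40^0.9 = 27.7
- 40^1.0 = 40
- 40^1.1 = 57.8

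The reader must compare each with 40.

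**4. Direction of the route ratio.** Character values sort as IV, SC, so the contrast is IV − SC. At a bioavailability of 0.40 it back-transforms to 1/0.40 = 2.50. The 90% interval is the ratio multiplied or divided by exp(1.812 × s × √(1/6 + 1/6)), where s = √ln(1 + CV²) and 1.812 is the t multiplier on 10 df. The CV is an assumption:

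| CV | SC/IV 0.40 | IV/SC 2.50 |
|---|---|---|
| 15% | 0.342–0.468 | 2.14–2.92 |
| 25% | 0.309–0.518 | 1.93–3.24 |
| 40% | 0.267–0.599 | 1.67–3.74 |

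Each right-hand interval is the exact reciprocal of the left. If route were instead numbered in the SAP section 6 treatment order (200 mg SC is 5, 200 mg IV is 6), the contrast would already be SC − IV.

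**5. Cmax label.** The sentence ends "explanatory variable and ratio (SC/IV), and its 90% CI will be calculated based on the model to assess the absolute bioavailability", for both responses. The AUC(0-∞) ratio at equal dose estimates the fraction absorbed, F. The Cmax ratio also depends on absorption rate. Assuming one compartment and an IV peak at the start of elimination, the Cmax ratio is F × exp(−(ln 2/10.5) × 3) = 0.40 × 0.820 = 0.33, although F is 0.40.

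**The case against.** The strongest reply is that the text is the specification. Both blocks are headed as examples, and code 1 contains placeholders, so it cannot be run as it stands. The text promises 90% intervals only for ratios, and those are right. It does not promise a slope. The route coding is not stated, the text names SC/IV explicitly, and a bioavailability printed as 2.5 would be noticed against the 40% in the protocol. The missing SolutionF table would be noticed at the first run. The Cmax ratio is computed as intended, so only its label is in question.

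Most of this stands, and it rules out a stronger reading. A reader might infer that the code fails to deliver the promised 90% intervals, that no dose-proportionality estimate is available, and that the bioavailability ratio will certainly be inverted. The documents do not support any of these. The promised levels are met, the slope follows by division, and the inversion depends on an unstated coding and loses no information. Nor can it be said that one table would mix coverage, since the TFL shells are not among the documents.

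What the reply does not remove is that the example code contradicts its own output request, that the direction of a stated ratio is left to chance, and that the wording on Cmax is wrong whatever the software does.

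**Conclusion.** The point holds as a minor correction to the SAP. Under standard PROC MIXED behaviour, code 1 does not create the slope table it requests, and its dose-mean limits are 95% where the other intervals are set to 90% (20% wider on the log scale overall, 22% within a population). If route is held as the characters IV and SC, code 2 yields the reciprocal of the stated ratio, 2.5 for 0.40. Independently of SAS, the Cmax ratio is not a measure of absolute bioavailability; the 0.33 against 0.40 illustration rests on a one-compartment assumption that the documents do not make.

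No data, fitted model, sample size or escalation rule is affected. The documents set no acceptance limit for the slope or for bioavailability.

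**What to change.** **Code 1.** Use `model lpk = ldose / s cl alpha=0.1 residual ddfm=kr;` and add `alpha=0.1` to the first ESTIMATE. State in the text that the slope will be reported with its 90% interval for each parameter. Dose-normalised ratios are optional.

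**Code 2.** Use `lsmeans route / alpha=0.1 cl diff=control('IV');` so that the contrast is SC minus IV, and state how route is coded, because the named control must match the stored value. An ESTIMATE with coefficients `route -1 1` is not a safe substitute: it depends on the same unstated level order.

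**Text.** Call only the AUC(0-∞) SC/IV ratio absolute bioavailability, and report the Cmax ratio as relative peak exposure.

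The cost is a few words of code and text. No new data are needed.

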11.2. Data Analysis Plans

11.2.1. General Considerations

Statistical analysis of this study will be the responsibility of Eli Lilly and Company or its designee.

PK analyses will be conducted on the full analysis set. This set includes all data from all randomized subjects receiving at least one dose of the IP according to the treatment the subjects actually received. Safety analyses will be conducted for all enrolled subjects, whether or not they completed all protocol requirements.

Additional exploratory analyses of the data will be conducted as deemed appropriate. Analyses will be fully detailed in the statistical analysis plan. Study results may be pooled with the results of other studies for population PK analysis purposes to avoid issues with post-hoc analyses and incomplete disclosures of analyses.

Data from subjects receiving placebo in the IV cohorts will be pooled to form 1 placebo group.

Data will be also summarized by race (Japanese and Caucasian) where appropriate.

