### **3. INTRODUCTION**

This SAP has been developed after review of the Clinical Study Protocol (final version dated 11 August 2015), and Amendment (a) (final version dated 23 January 2018).

This SAP describes the planned analysis of the safety, tolerability and pharmacokinetic (PK) data from this study. A detailed description of the planned TFLs to be presented in the clinical study report (CSR) is provided in the accompanying TFL shell document.

The intent of this document is to provide guidance for the statistical and PK analyses of data. In general, the analyses are based on information from the protocol, unless they have been modified by agreement between Eli Lilly and Company and Covance Early Clinical (EC) Biometrics. A limited amount of information concerning this study (e.g., objectives, study design) is given to help the reader's interpretation. This SAP must be signed off prior to first subject administration for this study. When the SAP and TFL shells are agreed upon and finalized, they will serve as the template for this study's CSR.

This SAP supersedes the statistical considerations identified in the protocol; where considerations are substantially different, they will be so identified. If additional analyses are required to supplement the planned analyses described in this SAP, they may be performed and will be identified in the CSR. Any substantial deviations from this SAP will be agreed upon between Eli Lilly and Company and Covance EC Biometrics and identified in the CSR. Any minor deviations from the TFLs may not be documented in the CSR.

This SAP is written with consideration of the recommendations outlined in the International Conference on Harmonisation (ICH) E9 Guideline entitled Guidance for Industry: Statistical Principles for Clinical Trials and the ICH E3 Guideline entitled Guidance for Industry: Structure and Content of Clinical Study Reports.

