## **11. CHANGES FROM THE PROTOCOL SPECIFIED STATISTICAL ANALYSES**

There were no changes from the protocol specified statistical analyses.

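### SAP 9.3.2 replaces the protocol's race-by-dose interaction model with separate fits per population and no between-population contrast, while SAP Section 11 reports no changes

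*SAP*

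**What the plan says.** Protocol 11.2.4.2 evaluates dose proportionality after IV dosing with a power model (log Cmax and log AUC on log dose). It then adds a second, exploratory step: "Exploratory power model analysis based on the model including race and race-by-dose interaction terms will be also performed". The stated aim is to see whether race affects dose proportionality.

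SAP 9.3.2 keeps the main power model and the aim but changes the second step: "The above analysis will also be repeated for each population separately to examine the effect of the population on dose proportionality". The example code for the analysis to be repeated is `model lpk = ldose / alpha=0.1 residual ddfm=kr`, that is, "model lpk = ldose / alpha=0.1 residual ddfm=kr", in which log dose is the only term. Its comparative statement, "estimate 'zz mg - xx mg' ldose pp / alpha=0.1 cl", contrasts one dose with another within a single fit.

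On departures from the protocol, SAP Section 3 says: "This SAP supersedes the statistical considerations identified in the protocol; where considerations are substantially different, they will be so identified". SAP Section 11 then says: "There were no changes from the protocol specified statistical analyses".

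**The concern.** The effect of population on dose proportionality is, in a power model, the difference between the Japanese and Caucasian slopes. The protocol's interaction term estimates that difference directly. The SAP's plan yields two slopes, each with its own 90% CI, and leaves the reader to combine them. Putting two intervals side by side does not give an interval for the difference.

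There is also a documentation fault. Section 11 is where a reader checks whether the protocol's analyses were kept. A model named in the protocol has been replaced by a different specification, and Section 11 says nothing was changed.

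At stake is the secondary objective of exploring PK in Japanese subjects relative to Caucasian subjects. The primary safety objective is not affected.

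**Working it through.** **Text comparison**

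| Item | Protocol 11.2.4.2 | SAP 9.3.2 |
|---|---|---|
| Purpose | Effect of race on dose proportionality | Effect of population on dose proportionality |
| Model | One model with race and race-by-dose terms | Dose-only model, fitted once per population |
| Population term or interaction | Yes | None |
| Contrast between populations | Available from the interaction coefficient | None; contrasts are between doses, or SC against IV |
| Declared as a change in SAP Section 11 | n/a | No |

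**Inputs for the size of the effect**

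The plan gives no precision figure for this comparison. Its only sample-size figure is about 50 subjects, and the cohort sizes reproduce it: 10 + 5 × 8 = 50.

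- IV doses (Protocol 9.3): 60, 200, 600, 1200 and 2400 mg.
- Japanese subjects on IV LY3074828 (SAP Section 5): 3, 3, 5, 3, 3 across those doses = 17.
- Caucasian subjects on IV LY3074828: 3 per dose × 5 = 15. Total 32.
- Between-subject CV: not given in the documents. Assumed 20%, 30% and 40%, equal in both populations.
- Residual SD on the natural-log scale: σ = √ln(1 + CV²) = 0.198, 0.294, 0.385.

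**Formulas and results**

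1. Sum of squares of log dose about its mean: S_J = 25.81 and S_C = 25.69.
2. Slope SE in each population = σ/√S.
3. SE of the slope difference = √(SE_J² + SE_C²).
4. Interaction model: 32 − 4 = 28 residual df. The 90% CI half-width is t(0.95, 28) × SE, with t = 1.7011.
5. Separate fits: 17 − 2 = 15 and 15 − 2 = 13 df. Combining them by Welch–Satterthwaite gives 27.85 df.
6. Over the IV range, 2400/60 = 40 and ln 40 = 3.689. The half-width translates to a factor exp(half-width × 3.689) on the change in the Japanese/Caucasian exposure ratio from the lowest to the highest dose.

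| Assumed CV | SE_J | SE_C | SE of difference | Half-width, interaction model | Half-width, rebuilt from separate fits | Factor over 40-fold range |
|---|---|---|---|---|---|---|
| 20% | 0.0390 | 0.0391 | 0.0552 | 0.0939 | 0.0939 | 1.41 |
| 30% | 0.0578 | 0.0579 | 0.0818 | 0.1392 | 0.1392 | 1.67 |
| 40% | 0.0758 | 0.0760 | 0.1074 | 0.1827 | 0.1827 | 1.96 |

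Fitting both ways to one simulated dataset gave an interaction coefficient of −0.063877 and a difference of the separate slopes of −0.063877, as the algebra requires.

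If a reader instead judged by whether the two 90% CIs overlap, the slopes would have to differ by about the sum of the separate half-widths: 0.1375, 0.2039 or 0.2676 at the three CVs, against 0.0939, 0.1392 or 0.1827 for the direct contrast. Neither document proposes an overlap rule. The comparison only shows why two separate intervals do not replace an interval for the difference.

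**The case against.** The strongest reply is that nothing statistical has been lost. Separate fits have the same mean structure as the full interaction model, give the same slopes, and let each population keep its own residual variance. This is correct. The half-widths and factors above therefore describe how imprecise a small exploratory comparison is, whichever method is used; they are not a cost of the SAP's choice.

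Second, the protocol names model terms but no CI for the slope difference, and it states that the numbers do not support a formal ethnic comparison. The SAP also plans PK summaries by population, and its other estimate statement gives a fitted value at each dose, so side-by-side description is available. This is a fair limit on the weight of the point. None of that output, however, is the slope difference with its uncertainty, which an interaction model would normally supply.

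Third, the sponsor may change the method. The protocol leaves the detail to the SAP ("Analyses will be fully detailed in the statistical analysis plan"), the SAP supersedes the protocol, and further analyses are permitted ("they may be performed and will be identified in the CSR"). The sponsor could add that equivalent fits are not a substantial difference in the sense of SAP Section 3. That argument has some force against the Section 3 promise but does not rescue Section 11, which is unqualified. Permission to run unspecified extra analyses does not plan the interaction model either.

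Finally, the code is labelled an example, and the TFL shells are not among the documents, so a contrast there cannot be excluded. The narrative sentence in 9.3.2 specifies separate fits independently of the code, and shells could not make Section 11 accurate.

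**Conclusion.** The point holds, at minor severity. On the SAP text, a model the protocol committed to has been replaced, no direct estimate is planned for the effect the SAP says it examines, and Section 11 wrongly reports no changes. The change of method is allowed; what is missing is its declaration and the contrast.

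The practical effect is small. The analysis is exploratory and serves a secondary objective, no decision rule depends on it, and the slope difference can be recovered from the separate fits with the same interval width. The estimate would be imprecise in any case: the change in the exposure ratio over the 40-fold dose range would be known to within a factor of about 1.4 to 2.0. Those figures rest on the planned allocation with all 32 subjects evaluable, equal variances, and an assumed CV of 20% to 40%. The finding about the text depends on none of these assumptions.

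**What to change.** 1. In SAP 9.3.2, fit the protocol's model to all IV LY3074828 subjects and report the slope difference with its 90% CI, labelled exploratory. For example: `class pop; model lpk = ldose pop pop*ldose / ddfm=kr; estimate 'slope difference, Japanese - Caucasian' pop*ldose -1 1 / alpha=0.1 cl;` with levels in alphabetical order. Keep the per-population fits as supportive.
2. Correct SAP Section 11 to list any departure that remains.

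If the sponsor prefers the separate fits, Section 11 should state and justify the replacement. Section 9.3.2 should then report the slope difference from those fits, with SE = √(SE_J² + SE_C²) and Satterthwaite df, which gives the same half-width at the planned numbers under equal variances.

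The cost is a few lines of code and text in 9.3.2 and one sentence in Section 11. No new data are needed.
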